### **3.5.4 Comprehensive Skin Examination**

Comprehensive skin examinations will also be performed per the SOA. Normal and abnormal findings regarding skin lesions will be assessed. At each visit skin hyperpigmentation, changes in skin tone, new mole development, and changes in existing moles will be assessed.

### **3.5.5 Electrocardiogram (ECG)**

A single 12-lead ECG recording will be performed as specified in the SOA. If an ECG is not practical in a young patient, it may be replaced by a rhythm strip and only HR and PR interval will be collected. The following items will be measured:

- HR (beats/min)
- PR interval (msec)
- QRS interval (msec)
- QT interval (msec)
- QTcF interval (msec)
- Overall Interpretation (Normal, Abnormal – Not Clinically Significant (NCS), Abnormal – CS)

### **3.5.6 Clinical Laboratory Tests**

Hematology, clinical chemistry, and urine analysis laboratory tests will be performed as specified in the SOA. At each applicable visit, the laboratory tests will be collected prior to study treatment. Due to the age of the children, it may not be possible to collect all labs at every study visit. Screening may be performed over multiple days, to complete the required assessments. After enrollment, if all lab tests are not possible, then the tests

should be collected in the following descending order of priority: safety, anti-drug antibodies, trough PK, hemoglobin A1c and then lipid panel.

### **3.5.7 Injection Site Examination**

At each visit where study treatment is administered, the injection site will be evaluated. The injection site evaluation will include:

- Reaction (Erythema, Edema, Induration, Itching, Pain or Tenderness, Other)
  - Length (Erythema, Edema, Induration only)
  - Width (Erythema, Edema, Induration only)
- Finding (None, Mild, Moderate, Severe)
- Clinically significant (Yes, No)

### **3.5.9 Ages & Stages Questionnaires®, Third Edition (ASQ®-3)**

The ASQ®-3 is a developmental screening tool that assesses developmental progress in children between one month to 5 ½ years. The ASQ®-3 is intended for use at six-month intervals between 6 months and 3 years of age, and then at one-year intervals through age 5. Thus, for patients who enter the study at ages between 2 years and 3 years, the ASQ-3 will be administered at the Enrollment (Baseline) Visit, Week 28 visit and EOT Visit. For patients who enter the study between the ages of 3 and 6 years old, the ASQ-3 will only be administered at the Enrollment (Baseline) Visit and EOT Visit.

The ASQ-3 consists of five areas: communication, gross motor, fine motor, problem solving, and personal-social. Each area consists of six questions that are scored Yes = 10 points, Sometimes = 5 points, and Not yet = 0 points. The 10 free-response items will not be analyzed.

[figure not shown]
[figure not shown]
[figure not shown]
The total area score is calculated by first adding up the questions within each area and then comparing the total area score to the respective cutoff score on the ASQ-3 scoring sheet to be normalized to one of three categories, which indicate whether the child's development appears to be on schedule.

[figure not shown]
- Below the cut-off = Further assessment with a professional may be needed.
- Close to the cut-off = Providing learning activities and monitor.

[figure not shown]
- Above the cut-off = The child's development appears to be on schedule.

The following table presents ASQ-3 Referral cutoff scores and monitoring zone cutoff scores used in the analysis:

PARCAT2	PARAM	Referral Cutoff	Monitoring zone Cutoff
30 Month Questionnaire	Communication - 30	33.30	43.56
36 Month Questionnaire	Communication - 36	30.99	41.43
42 Month Questionnaire	Communication - 42	27.06	38.54
48 Month Questionnaire	Communication - 48	30.72	41.82
54 Month Questionnaire	Communication - 54	31.85	42.82
60 Month Questionnaire	Communication - 60	33.19	42.80
30 Month Questionnaire	Gross Motor - 30	36.14	44.84
36 Month Questionnaire	Gross Motor - 36	36.99	45.84
42 Month Questionnaire	Gross Motor - 42	36.27	45.15
48 Month Questionnaire	Gross Motor - 48	32.78	42.74
54 Month Questionnaire	Gross Motor - 54	35.18	44.58
60 Month Questionnaire	Gross Motor - 60	31.28	41.72
30 Month Questionnaire	Fine Motor - 30	19.25	33.02
36 Month Questionnaire	Fine Motor - 36	18.07	32.57
42 Month Questionnaire	Fine Motor - 42	19.82	33.68
48 Month Questionnaire	Fine Motor - 48	15.81	30.58
54 Month Questionnaire	Fine Motor - 54	17.32	31.72
60 Month Questionnaire	Fine Motor - 60	26.54	39.05
30 Month Questionnaire	Problem Solving - 30	27.08	38.63
36 Month Questionnaire	Problem Solving - 36	30.29	41.13
42 Month Questionnaire	Problem Solving - 42	28.11	39.82
48 Month Questionnaire	Problem Solving - 48	31.3	42.04
54 Month Questionnaire	Problem Solving - 54	28.12	39.68
60 Month Questionnaire	Problem Solving - 60	29.99	41.29
30 Month Questionnaire	Personal - Social - 30	32.01	41.94
36 Month Questionnaire	Personal - Social - 36	35.33	44.07
42 Month Questionnaire	Personal - Social - 42	31.12	41.25
48 Month Questionnaire	Personal - Social - 48	26.6	38.47
54 Month Questionnaire	Personal - Social - 54	32.33	42.55
60 Month Questionnaire	Personal - Social - 60	39.07	46.96

#### **4 General Analysis Conventions**

[Redacted text block]

[Redacted text block] Data for all patients in the clinical database will be included in the data listings. Calculated (derived) variables will be listed as appropriate.

All efficacy, safety and baseline characteristics variables will be presented using descriptive statistics and figures as appropriate. Continuous variables will be summarized using descriptive statistics (number of observations, mean, standard deviation (SD), median, minimum, and maximum). Categorical variables will be presented in frequency tables with number and percent of observations for each level. Missing counts for all variables will be presented for informational purposes only and will not be included in percentage calculations.

Study days will be calculated relative to the first injection of study drug. Day 1 will be the first day of study drug administration in the study. In data listings, the relative study day (in relation to date of first study drug administration) of all dates will be presented.

AEs, medical history events, and concomitant treatments/procedures will be coded using Medical Dictionary for Regulatory Activities (MedDRA), Version 24.0 or higher. Prior/concomitant medications will be coded using the World Health Organization (WHO) Drug Dictionary Global B3, March 2021 or higher.

Any changes from the SAP will be detailed in the Clinical Study Report (CSR).

## 4.1 Study Periods

The study has two periods: Screening and Treatment.

- Screening Period – From providing informed consent to just before the Enrollment (Baseline) Visit (Day 1). Can range between 56 – 1 day(s) prior to the Enrollment (Baseline) Visit.
- Treatment Period - From the Enrollment (Baseline) Visit to EOT (Day 365, or date of withdrawal).

A final EOS visit will occur on Study Day 393 and will be conducted via telephone. Patients may be eligible to enroll into a long-term extension study.

## 4.2 Visit Windows

Study visits are expected to occur according to the protocol schedule ([Section 16.1](#)). Efficacy by-visit summaries and analyses will use analysis visits. Both scheduled and unscheduled visits (including early termination visit) will be windowed based on the following analysis visit windows.

Analysis Visit	Target Study Day	Analysis Visit Window
Baseline	1	≤ 1
Week 2	15	2 – 22
Week 4	29	23 – 36
Week 6	43	37 – 50
Week 8	57	51 – 71
Week 12	85	72 – 99

Week 16	113	100 – 127
Week 20	141	128 – 169
Week 28	197	170 – 225
Week 36	253	226 – 281
Week 44	309	282 – 337
Week 52	365	338 – 379
Week 56	393	≥ 380

If two or more assessments (include both scheduled and unscheduled assessments) are available for the analysis visits, then all assessments will be included in data listings and the following rule will be applied for determining the values to be used for the summaries and analyses in tables:

- Efficacy assessments: the assessment taken closest to the target study day will be used for the summaries and analyses; if two visits are equally distant to the target study day, then the more recently occurring visit will be chosen (i.e. If the target study day was 01 JAN 2021 and Visit A occurred on 27 DEC 2020 and Visit B occurred on 06 JAN 2021 (both 5 days apart from the target study day), then Visit B will be chosen).

Safety by-visit summaries and analyses will use the nominal evaluation visit, as recorded on the eCRF. Both scheduled and unscheduled visits (including early termination visit) will be windowed based on the protocol-specified windows outlined in [Section 16.1](#). If two or more assessments (include both scheduled and unscheduled assessments) are available for the visits, then all assessments will be included in data listings and the following rule will be applied for determining the values to be used for the summaries and analyses in tables:

- Safety assessments, including clinical laboratory tests: the scheduled visit will be used over any unscheduled visits conducted within window; otherwise, the latest assessment will be used for the summaries and analyses.

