## 2. SCHEDULE OF ASSESSMENTS

**Table 1: Schedule of Assessments**

Assessment	Screening	Enrollment Visit (Baseline)	Dose Escalation Visits 	Trial Visits 	EOT	EOS 	ETT	Bridging Visits
Trial Week	-8 to -1		2, 4, 6	8, 12, 16, 20, 28, 36, 44 	52	56		Q12 Weeks (If needed, In Person)
Trial Day	-56 to -1	1	15, 29, 43	57, 85, 113, 141, 197, 253, 309	365	393		
Window			±3	±5	±5	±3		
Informed Consent	X							
Inclusion/ Exclusion	X	X						
Medical History	X	X						
Physical Examination 	X	X*	X	X	X		X	X
Fitzpatrick classification scale		X			X		X	
Comprehensive Skin Examination 	X	X		X	X		X	X
Weight 	X	X	X	X	X		X	X
Height 	X	X	X	X	X		X	X
Vital Signs 	X	X	X	X	X		X	X
ECG 	X	X	X	X (W8 and 44)	X		X	X
Daily drug compliance 		X	X	X	X		X	
Genetic Sample 		X						
Safety Lab Tests 	X	X	X	X	X		X	X

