**Table 1: Schedule of Assessments**

Assessment	Screening	Enrollment Visit (Baseline)	Dose Escalation Visits 	Trial Visits 	EOT	EOS 	ETT	Bridging Visits
Trial Week	-8 to -1		2, 4, 6	8, 12, 16, 20, 28, 36, 44 	52	56		Q12 Weeks (If needed, In Person)
Trial Day	-56 to -1	1	15, 29, 43	57, 85, 113, 141, 197, 253, 309	365	393		
Window			±3	±5	±5	±3		
Ages & Stages Questionnaires, Third Edition (ASQ-3) 		X		X	X			X
Dispense Trial Drug		X	X	X	X**			X
Return Trial Drug			X	X	X		X	X

Abbreviations: ECG=electrocardiogram; EOS=End of Study; EOT=end of treatment; ETT=Early Termination of Treatment; [REDACTED]; LTE=Long-term extension; [REDACTED]

\*Note: If there are <2 weeks between screening and enrollment, the enrollment visit physical examination may be waived.

\*\*Drug is dispensed at the EOT only for patients who continue to the Bridging visits.

 Patients should attend dose-escalation visits as appropriate per their respective escalation regimen, which is dictated by their weight, until achieving maximum dose level. See Section 7.3 for details.

 The dose may continue to be evaluated and adjusted, at the discretion of the Investigator, in 0.5 mg increments, so long as the daily dose is kept between 0.5 mg and the weight-based maximum for the patient (see Table 3).

 EOS visit should occur within 4 weeks of the last dose of study drug for patients who either discontinue prematurely or for patients who are being monitored for an adverse event (AE) after the EOT. This visit is not required for patients who complete the Week 52 visit and either enroll in the LTE or transition to Bridging visits.

 A complete physical examination will be conducted at screening and at the EOT visit. At other timepoints, an abbreviated examination will be performed. The abbreviated examination should focus on heart, lungs, skin, neurologic exam, and any areas of previous abnormal findings, noting any changes from baseline. Tanner staging should be performed at Screening and at the EOT (Week 52) visit. It may be done at additional visits, at the discretion of the Investigator

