#### **5.1.4. End of Treatment**

The End of Treatment (EOT) will occur as an in-person clinic visit on Trial Week 52, which is the final day of treatment with setmelanotide. At the EOT, patients who are considered likely to benefit from continued setmelanotide treatment and who have completed this trial may be eligible to enter an open-label long-term extension (LTE) trial with setmelanotide. Patients must meet the eligibility criteria and should discuss eligibility with the Investigator. Eligible patients may participate in Bridging visits (every 12 weeks) (Table 1) if the LTE is not yet active.

All patients who discontinue treatment prematurely should attend an Early Termination of Treatment visit (ETT) as soon as possible after the last dose of trial treatment. Patients who discontinue treatment but remain enrolled in the trial should continue to complete all assessments (as Retained Dropouts). These patients will be required to complete the End of Study (EOS) as applicable following the ETT (Section 5.1.5). Patients who discontinue treatment prematurely but remain enrolled and complete assessments through Week 52 are eligible to enroll in the optional LTE trial.

Patients who discontinue prematurely and withdraw from the trial will not be required to complete the EOS visit following the ETT. If the ETT visit occurs 4 weeks or later following the last dose of Setmelanotide, then the ETT visit will replace the EOS visit if no AEs are being monitored.

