### 9.1 Primary Efficacy Endpoints

#### 9.1.1 Proportion of Patients with a Decrease from Baseline to 52 Weeks in BMI Z-score $\geq 0.2$

A “responder” is defined as a decrease from baseline to 52 weeks in the patient’s BMI z-score of  $\geq 0.2$ . The WHO Child Growth Standards 2007 will be used for BMI z-score. At each visit, an indicator variable will be created to identify patients that have a decrease in BMI z-score from baseline of 0.2 or more, allowing for the analysis of proportion of patients who meet the “responder” definition. The proportion and the corresponding 2-sided 95% CI using the Clopper-Pearson method will be reported for each visit. Sample SAS code to calculate the BMI z-score can be found at <https://www.who.int/tools/child-growth-standards/software>.

#### 9.1.2 Mean Percent Change in BMI from Baseline to Week 52

For the analysis of Mean percent change in BMI from baseline, percent changes in BMI from baseline over time will be summarized using descriptive statistics. Mean percent change in BMI from baseline over time will also be provided graphically. A 2-sided 95% CI with Student’s *t*-distribution will be provided for Mean percent change in BMI from baseline. In addition, patient figures showing the percent change in BMI from baseline will be created. Information on the patient’s baseline BMI will be included in the figure.

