## **15 References**

## 16 Appendices

### 16.1 Schedule of Assessments

Assessment	Screening	Enrollment Visit (Baseline)	Dose Escalation Visits 	Study Visits	End of Treatment Visit	End of Study Visit (Telephone)	Early Termination Visit
Study Week	-8 to -1		2, 4, 6	8, 12, 16, 20, 28, 36, 44 	52	56	
Study Day	-56 to -1	1	15, 29, 43	57, 85, 113, 141, 197, 253, 309	365	393	
Window			+/-3	+/-5	+/- 5	+/-3	
Informed Consent	X						
Inclusion/ Exclusion	X	X					
Genetic Sample 		X					
Medical History	X						
Physical Exam 	X	X*	X	X	X		X
Fitzpatrick classification scale		X			X		X
Comprehensive Skin Exam 	X	X		X	X		X
Weight 	X	X	X	X	X		X
Height 	X	X	X	X	X		X
Waist circumference 	X	X	X	X	X		X
Vital Signs 	X	X	X	X	X		X
ECG 	X	X	X	X 	X		X
Daily drug compliance 		X	X	X	X		
Adverse events	X	X	X	X	X	X	X
Injection site inspection		X	X	X	X		X
Concomitant medication Review	X	X	X	X	X	X	X
Optional Nutritional Counseling 		X	X	X	X		
Bone Age 		X			X		
Ages & Stages Questionnaires, Third Edition (ASQ- 3) 		X		X	X		

Assessment	Screening	Enrollment Visit (Baseline)	Dose Escalation Visits 	Study Visits	End of Treatment Visit	End of Study Visit (Telephone)	Early Termination Visit
Study Week	-8 to -1		2, 4, 6	8, 12, 16, 20, 28, 36, 44 	52	56	
Study Day	-56 to -1	1	15, 29, 43	57, 85, 113, 141, 197, 253, 309	365	393	
Window			+/-3	+/-5	+/- 5	+/-3	
Safety Lab Tests 	X	X	X	X 	X		X

[figure not shown]
[figure not shown]

Anti-Drug Antibodies 	X			X 	X		X
PK profile 		X 		X 			X
Trough PK 			X	X 	X		
Dispense Study Drug		X	X	X			
Return Study Drug			X	X	X		
Optional Informed Consent for Exit Interviews					X		

Abbreviations: ECG=Electrocardiogram

Note: If there are <2 weeks between screening and enrollment, the enrollment visit physical examination may be waived.

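### The SAP's Week 56 efficacy window has no upper limit, so by the visible rule on-drug Bridging measurements from about Week 64 would be reported as Week 56

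*SAP*

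**What the plan says.** SAP 4.2 assigns efficacy assessments to analysis visits by study day: "Both scheduled and unscheduled visits (including early termination visit) will be windowed based on the following analysis visit windows". Where a window holds more than one assessment, "the assessment taken closest to the target study day will be used for the summaries and analyses". The Week 52 window is Days 338 to 379. The Week 56 window has target Day 393 and starts at Day 380, with no end.

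SAP 4.1 describes the visit itself: "A final EOS visit will occur on Study Day 393 and will be conducted via telephone". Protocol 5.1.5 makes the telephone optional, for patients with no adverse event under monitoring. In both schedules (protocol Table 1, SAP 16.1) the weight and height cells for that visit are blank.

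Protocol Table 1 has a further column for in-person Bridging visits every 12 weeks, with weight and height marked. A note to that table says: "Drug is dispensed at the EOT only for patients who continue to the Bridging visits". Another note to Table 1 and protocol 5.1.5 both say that patients who move to Bridging need no End of Study visit. SAP 16.1 has no Bridging column. The visible SAP mentions Bridging once, in Section 12, to set the interim cut-off.

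The windows feed by-visit results. For the responder endpoint, SAP 9.1.1 says: "The proportion and the corresponding 2-sided 95% CI using the Clopper-Pearson method will be reported for each visit". SAP 9.1.2 plots mean percent change in BMI over time, and SAP 9.2.2 summarizes weight at each visit and graphs its change.

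**The concern.** The SAP sets up an efficacy analysis visit at a time when no efficacy measurement is scheduled, and leaves its window open to the right. The only scheduled weights and heights that fall there routinely are those from Bridging visits.

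A reader of a table or figure would take Week 56 as follow-up 4 weeks after treatment stopped. Under the visible rule the row could hold on-drug values from about 12 weeks after Week 52. They would also come from a selected group, because protocol 5.1.5 offers continued treatment to patients who tolerated the drug well and are thought likely to benefit. Such a row could be misread as an effect that lasts after stopping. With 10 to 15 patients planned, a few values could make up the whole row.

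**Working it through.** **Inputs.** Analysis windows: SAP 4.2. Week 52 visit on Day 365 ±5, End of Study on Day 393 ±3, and Bridging every 12 weeks: protocol Table 1. A ±5-day window for Bridging appears in one of the three parts of Table 1 and is blank in the other two. The documents do not say from which day the 12 weeks run, so Day 365 is assumed and the range over the Week 52 visit window is also shown.

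**1. Reproduce the SAP's windows.** Target day = 7 × week + 1, so Week 52 is Day 365 and Week 56 is Day 393. From Week 2 to Week 52, each upper limit is the midpoint between neighbouring targets. For Week 52, (365 + 393)/2 = 379, as stated. Week 56 has no later target, and its window was left open.

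**2. Place the first Bridging visit.** 365 + 84 = Day 449, and (449 − 1)/7 = Week 64. With ±5 days this is Day 444 to 454. Counted instead from a Week 52 visit held on Day 360 to 370, the range is 360 + 84 − 5 = 439 to 370 + 84 + 5 = 459. Later visits, counted from Day 365, fall on Days 533 and 617 (Weeks 76 and 88).

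**3. Apply the rule.** All these days are 380 or later, so all map to Week 56. The closest-to-target rule picks the first Bridging visit unless something nearer exists. No scheduled measurement does, because Week 56 has no weight or height and Bridging patients may skip that visit.

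**4. Size of the mislabelling.**
- Past the Day 393 target: 444 − 393 = 51 to 454 − 393 = 61 days (46 to 66 with the Week 52 visit window).
- After Day 365: 79 to 89 days, under a label that implies 393 − 365 = 28.
- Largest distance from target in every other post-baseline window: 28 days (the upper side of Weeks 20, 28, 36 and 44).
- Ratio: 51/28 = 1.8 to 61/28 = 2.2 (46/28 = 1.6 to 66/28 = 2.4 with the Week 52 visit window).

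**5. Check the primary time point.** The Week 52 window ends at Day 379. The earliest first Bridging day is 439, so Bridging data cannot enter it.

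**6. Check a closed window.** The lower limit is 393 − 380 = 13 days below target, and a symmetric upper limit is 393 + 13 = Day 406. The End of Study visit (Days 390 to 396) stays inside. The earliest first Bridging day is 439 − 406 = 33 days outside.

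**The case against.** The best counter-argument is that Bridging data were never meant to enter these summaries. The windowing paragraph in SAP 4.2 itself refers to the schedule in SAP 16.1, which has no Bridging column. SAP 4.1 knows only a Screening and a Treatment Period and ends the latter at End of Treatment. Protocol 5.1.5 offers Bridging for the case that the extension is not open when the patient completes the trial, which places it after completion. Part of SAP Section 4 is redacted and could hold a rule on which data are included. This stands as evidence of possible intent, and a reader who inferred that the SAP plans to pool Bridging data would go beyond the documents. It does not settle the matter. None of the visible text is an exclusion, protocol Table 1 lists Bridging among the trial's visits, and the Week 56 row itself lies after the Treatment Period.

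A second argument is that the row has a proper use. SAP 4.2 windows the early termination visit, at which weight and height are taken, and protocol 5.1.4 lets such a visit replace End of Study if it falls 4 weeks or more after the last dose and no adverse event is being monitored. A patient whose last dose was on Day 352 would reach that point on Day 352 + 28 = 380, within Week 56 and off drug. This stands, and is why the row should not simply be deleted.

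Third, the consequence is small: no hypothesis is tested, and SAP Section 4 has the listings show the actual study day. That also stands. Only summary rows and figures would mislead.

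**Conclusion.** The point holds as a minor one. The visible rule in SAP 4.2 would put a first Bridging value, from about Day 449, into a row that reads as 28 days off drug. This assumes that Bridging visits run from about Day 365, that they are recorded in this trial's database as their place in protocol Table 1 suggests, and that no redacted text excludes them. The day counts measure the error in the label and show no effect on any estimate. The number of Bridging patients is not given, and SAP 6 counts only those who go on to the extension study.

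Three stronger readings are not supported:
- **That the primary results are at risk.** Bridging data cannot reach the Week 52 window.
- **That the interim analysis is contaminated.** SAP 12 sets its cut-off before the first scheduled Bridging visit.
- **That last observation carried forward would fill the Week 56 row with Week 52 or earlier values.** SAP 9 does not say at which analysis visits it is applied, and a measurement never scheduled is arguably not missing. This is worth a side clarification at most and is not part of the point.

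**What to change.** In SAP 4.2, give the Week 56 efficacy window an upper limit, for example Days 380 to 406, symmetric about Day 393. Late early-termination and unscheduled off-drug values near the target are then kept under a fitting label. Add one sentence stating that Bridging measurements are either listed only or summarized under their own analysis visits (Week 64, 76 and so on). Word it to cover unscheduled weights in Bridging patients too, because one taken by Day 406 would still fall in the closed window.

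The cost is one table cell and one sentence. Values after the upper limit would appear only in listings or in separate rows. The Week 52 analyses and the conduct of the trial do not change. If exclusion was always intended, the edit merely records it.

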## **8.3. Safety Assessments**

### **8.3.1. Vital Signs**

Vital signs include systolic and diastolic blood pressure (BP), HR, respiration rate and body temperature (°C). Vital signs will be obtained in the sitting position following at least 5 minutes of rest at each time point designated in the SoA (Table 1).

All BP and HR measurements will be taken in triplicate, approximately 2 minutes apart. When possible, BP should be taken in the non-dominant arm throughout the trial, using the same methodology (automated or manual) and ensuring that an appropriately sized cuff is used.

Repeat measures and more frequent monitoring can be implemented for significant increases in BP or HR.

[figure not shown]

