#### **10.4 Clinical Laboratory Data**

Hematology, clinical chemistry, and urine analysis laboratory assessments, not discussed below in [Section 10.4.1](#), collected at each study visit and the changes from baseline to any post-baseline visit will be summarized by descriptive statistics. All laboratory tests will be compared to their laboratory normal range. Values outside of the normal range will be further classified as: Low – CS, High – CS, Low – NCS, High – NCS. Additionally, a shift table will be created to present any change from baseline in normal ranges in all laboratory tests across all post-baseline visits. This table will show the number and percentage of patients who had values that shifted from low - CS, low-NCS, normal, high – NCS, or high-CS at baseline to low - CS, low-NCS, normal, high – NCS, or high-CS at each post-baseline visit. Percentage of patients will be calculated using the number of patients with a baseline value and a non-missing value at the specified post-baseline visit as the denominator.

All laboratory data will be presented in data listings as collected. The listings will show the sample date, laboratory test, indicator test was not done (if applicable), reason test was not done (if applicable), laboratory value, and the change from baseline. Values outside of the reference range will be flagged with ‘H’ for high and ‘L’ for low, respectively.

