## 10.6 Electrocardiograms

The ECG and the changes from pre-dose baseline will be summarized descriptively at each visit. In addition, a shift table will be created to show any change from pre-dose baseline to each visit in the overall ECG interpretation.

QTcF interval prolongation will be presented separately as well. The number and percentage of patients with a QTcF interval of >450 msec, >480 msec, and >500 msec will be summarized by visit, along with the number and percentage of patients with a change from pre-dose baseline in QTcF interval of 30 - < 60 msec and  $\geq 60$  msec.

All ECG results will be presented in a data listing. The listing will show the assessment date, ECG measurement, indicator ECG was not done (if applicable), reason ECG was not done (if applicable) ECG value, the change from baseline.

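### The by-visit QTcF and laboratory shift tables can omit an extreme unscheduled value when a scheduled or later value shares its window, and no readable table counts children who ever crossed a threshold

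*SAP*

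**What the plan says.** **Choice of value.** For safety data, SAP 4.2 says: "the scheduled visit will be used over any unscheduled visits conducted within window; otherwise, the latest assessment will be used". Values not selected are still reported, since "then all assessments will be included in data listings".

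**Visit assignment.** SAP 4.2 says that "Safety by-visit summaries and analyses will use the nominal evaluation visit, as recorded on the eCRF", and that scheduled and unscheduled visits "will be windowed based on the protocol-specified windows outlined in" the SAP 16.1 schedule. Those windows are ±3 days at Weeks 2, 4 and 6 and ±5 days from Week 8 to Week 52.

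**ECG.** SAP 10.6 says that the number and percentage of patients "with a QTcF interval of >450 msec, >480 msec, and >500 msec will be summarized by visit". The same sentence covers changes from baseline of 30 to <60 msec and ≥60 msec. The shift table for overall ECG interpretation is also built visit by visit.

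**Laboratory.** SAP 10.4 tabulates shifts from the baseline category to the category at each later visit. On the denominator it says: "Percentage of patients will be calculated using the number of patients with a baseline value and a non-missing value at the specified post-baseline visit".

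**Adverse events.** Protocol 8.6.4 does not require clinically significant changes in laboratory values, blood pressure or pulse to be reported as adverse events, unless they are serious or lead to stopping of trial drug. ECG intervals are not named in that exemption.

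No readable section of the SAP gives a worst post-baseline or any-time-on-treatment count for ECG or laboratory data.

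**The concern.** One value per visit is a sensible choice for by-visit means. An outlier table has a different purpose: to show whether any child reached an extreme value. A rule that sets aside unscheduled values works against that purpose, because extra testing can be prompted by a safety concern. Protocol 8.3.1 says of vital signs: "Repeat measures and more frequent monitoring can be implemented for significant increases in BP or HR". Protocol 7.3 says that an unscheduled visit after a dose increase is unnecessary unless patient safety requires it.

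A second weakness remains even if no value is dropped. One child above a threshold at Week 4 and one at Week 8 may be the same child or two children, and by-visit rows cannot tell them apart.

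At stake is the number of children who crossed a QTcF or laboratory threshold. The trial has 10 to 15 children aged 2 to <6 years and no control arm, so a reader will look for that number.

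**Working it through.** The plan states no figure for this point, so there is none to reproduce. The check applies the SAP 4.2 rule literally to constructed cases. All QTcF values below are assumptions for illustration.

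**Inputs**
- Week 4 window: Day 29 ± 3 = Days 26 to 32 (SAP 16.1).
- Week 8 window: Day 57 ± 5 = Days 52 to 62 (SAP 16.1).
- ECGs are scheduled at Weeks 4 and 8 (Protocol Table 1).
- Planned N = 10 to 15 (SAP 3.4).

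**Main example, Week 4.** A scheduled ECG on Day 28 is normal, and an unscheduled ECG on Day 31 shows QTcF 505 msec. Both days lie in 26 to 32, so the scheduled value is kept. The table shows 0 of N above 500 msec; one child did exceed it.

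**Five patterns, Week 8 window**

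| Pattern | Values (msec) | Tabulated | Worst | Counted >500? |
|---|---|---|---|---|
| A | scheduled 440 (Day 57), unscheduled 510 (Day 60) | 440 | 510 | no |
| B | none scheduled; unscheduled 510 (Day 55), then 440 (Day 60) | 440 | 510 | no |
| C | unscheduled 510 (Day 58) only | 510 | 510 | yes |
| D | none scheduled; unscheduled 440 (Day 55), then 510 (Day 60) | 510 | 510 | yes |
| E | scheduled 510 (Day 57), unscheduled 440 (Day 60) | 510 | 510 | yes |

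The rule counts the 510 msec value in three of the five patterns; a worst-value row counts it in all five. The results at >450 and >480 msec are the same. The three-to-two split describes the constructed cases and is not an estimate of frequency.

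**Size per child.** 1/15 = 6.7% and 1/10 = 10%. Where a by-visit denominator is smaller than N, one child weighs more.

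**Ambiguity without a per-patient count.** One case in each of two visit rows is either one child (1/15 = 6.7% to 1/10 = 10%) or two (2/15 = 13.3% to 2/10 = 20%).

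**Values outside every window.** The windows for Weeks 2 to 52 cover 3 × 7 + 8 × 11 = 109 of the 369 days from Day 2 to Day 370, or 29.5%. SAP 4.2 gives no rule for placing an unscheduled value from the other days in a by-visit safety table. A worst-value row would not depend on that.

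**The case against.** Three stronger readings are tempting, and the documents do not support them.

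**That every extreme unscheduled value is deleted.** Patterns C and D show otherwise: an unscheduled extreme that is the only or latest value in its window is tabulated. No value is lost from the report, since all assessments are listed.

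**That the rule biases all safety summaries toward normal.** This is not shown. Pattern E keeps an abnormal scheduled value over a normal recheck, and pattern D keeps a worsening value. Neither document says how often unscheduled tests occur or which way they run.

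**That the value can survive only in a listing.** An abnormal value that is serious or leads to stopping of trial drug must be recorded as an adverse event. The Protocol 8.6.4 exemption does not name ECG intervals, so a QTcF of 505 msec could be recorded under the general definition and reach the adverse event tables. No readable text requires that, however, and the route is weaker for laboratory values that meet neither condition.

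It is also fair to say that ECG is not among the protocol endpoints or the safety endpoints in SAP 10.1, that the laboratory endpoint is a mean change, and that listings for 10 to 15 children can be read child by child. These points limit the importance of the gap. They do not correct the counts: SAP 10.6 chose to report threshold counts, and under its own rule those can be too low.

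SAP 4.2 does not say whether the nominal visit or the window prevails for an unscheduled assessment. This does not rescue the main example. If the Day 31 ECG kept an unscheduled label, it would still be absent from the Week 4 row.

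**Conclusion.** The point holds in conditional form. An extreme unscheduled value is omitted from the by-visit QTcF and laboratory tables when a scheduled value, or failing that a later assessment, falls in the same protocol window. Separately, no readable table states how many children ever crossed a threshold.

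Each omitted child moves a count by 6.7 to 10 percentage points at the planned N of 10 to 15; a supplemental cohort would reduce that share. The frequency is unknown, so this is the size per child and not an estimate of total bias.

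The QTcF part is firm, because SAP 10.6 can be read. The laboratory part is less certain: SAP 10.4.1 is not visible, part of the SAP section 4 conventions is redacted, and the table shells are in a separate document. A worst-value laboratory summary in one of those places cannot be excluded. The change is worth making because it is cheap and uses data already collected.

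**What to change.** Keep the SAP 4.2 rule for by-visit summaries. Add a per-patient row, labelled any time on treatment, based on the worst post-baseline on-treatment value from all scheduled, unscheduled and early-termination assessments:

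- **SAP 10.6:** children with QTcF >450, >480 and >500 msec, and with a change of 30 to <60 or ≥60 msec, each child classified by the largest value or change. The denominator is children with at least one post-baseline QTcF (and a baseline QTcF for the change categories), because SAP 3.5.5 allows a rhythm strip that yields no QTcF.
- **SAP 10.4:** shift from baseline to the worst value, with worst defined separately for low and high.

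SAP 10.5 needs no change, since it plans no outlier or shift table for vital signs. If SAP 10.4.1 or the table shells already contain a worst-value laboratory summary, a cross-reference is enough for that part.

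The cost is a short SAP edit and a few programmed rows, with no new data. The downside is that children with more unscheduled tests have more chances to show an extreme value; a footnote should say so.
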